7.1 Case Report Forms

The Biometrics and Outcomes Research Core (BORC) in the Department of Biostatistics at the University of Michigan is responsible for data management and analysis. It is the data coordinating center for several multi-center trials.

Case report forms are developed by the data coordinating center (DCC) and published on the ChiLDREN password-controlled website. The case report forms do not contain any personal subject identifiers, except dates, such as date of birth, which are necessary for research purposes. As needed, the coordinator prints the forms for each subject. The forms are completed and then countersigned by the investigator or study coordinator.

A combination of web-enabled and centralized data entry and management will be used. After the case report forms for a visit are completed, the research coordinator will enter a limited set of data into a web-enabled data management system.

Original case report forms will be securely maintained at the clinical sites. Clean copies of the case report forms will be transmitted monthly to the DCC to be entered into the study database. The forms entered into the database by the coordinator will not be transmitted to the DCC. Forms with personal identifiers are not sent to the DCC.

7.2 Quality Assurance:

The Project Manager/Clinical Monitor will review all data submitted to the DCC for accuracy and completeness. The Project Manager/Clinical Monitor will communicate with the study coordinators at each site about queries generated by the DCC and address all questions and concerns regarding the study protocol and problems with data entry or specimen sample shipment. Site visits will be made at 2 year intervals. Interim site visits may be made to centers with low compliance or high error rates. Performance reports will be generated quarterly to investigators and study coordinators at each center, as well as to DSMB.

7.3 Training

The Project Manager will develop a manual of operations to assist study coordinators at each center in following the protocol, entering and transferring data, and collecting, processing and shipping samples. The Project Manager/Clinical Monitor will be responsible for training the study coordinators at each center about the study protocol, the completion of source documents, the use of the web-based data entry system, and proper procedures with shipping samples to the central repository. Test runs of data entry into the web-based data entry system as well as sample shipment will be organized prior to site initiation. The Project Manager/Clinical Monitor will review the study protocol and data entry system, and check all regulatory documents prior to site initiation. A meeting for all investigators and study coordinators may be held in conjunction with the initiation of the study. In-service training for all study coordinators

will be held quarterly via conference calls to review frequently encountered questions regarding the protocol, data entry or sample processing.

8. Adverse Events

Since this is an observational study, in general there are no adverse events that can be attributed to it except at the time of blood draws. Whenever possible, blood samples will be obtained in conjunction with clinical samples. When not possible, such as for the parents, the bruising at the time of blood draws may be attributable to this study.

Although mechanisms for reporting serious adverse events have been established, it is anticipated that there will not be any serious adverse events that can be attributed to this study – there will be serious adverse events that are expected clinically in this study population. The only serious adverse events related to the performance of this study are those related to phlebotomy.

An adverse event (AE) is any unfavorable, harmful or pathological change in a research subject as indicated by symptoms, physical signs and/or clinically significant laboratory abnormalities that occur in association the study procedures. This definition includes intercurrent illness, injuries, exacerbation of pre-existing conditions. Stable pre-existing conditions and elective procedures to address such conditions are not adverse events. A change in a laboratory variable is considered an adverse event if it was considered by the investigators to be clinically significant (that is, if it institutes a diagnostic evaluation or indicates additional therapy is necessary).

The term serious is based on patient outcome associated with events that could threaten a patient's life or functioning. An event should be considered serious if it results in any of the following:

- Death,
- Life-threatening (patient was at risk of death as a result of the event, does not include hypothetical risk of death if the event had been more severe),
- Inpatient hospitalization or prolongation of existing hospitalization,
- Persistent or significant disability or incapacity,
- Congenital anomaly or birth defect,
- Medical or surgical interventions required to prevent one of the outcomes listed above.

The phrase 'related to study' implies causality or attribution to the study procedures. For purposes of defining as SAE, if a causal relationship cannot be ruled out, then an AE should be considered 'related to the study procedure(s)'. As noted above, it is very unlikely that any adverse events will be attributable to this study.

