2. unstained paraffin-embedded slides of the native liver

NOTE: Consent for this procedure may be included in the initial written informed consent or obtained by a separate informed consent prior to the procedure to conform with the IRB requirements at the clinical site.

In children where consent for DNA and cell lines has been obtained, at the time of transplantation or surgery the following may be obtained:

3. Skin from the surgical incision to establish cell lines and extract DNA.

NOTE: When an investigator believes that it is unlikely that whole blood will be available at either time (either due to the health of the child or due to the risk of loss-to-follow up), skin from the incision (approximately 1cm in length and 3 mm in width) may be removed and sent to the repository to establish cell lines and extract DNA. This method should be used rarely since the success rate for establishing cell lines from skin fibroblasts is much lower than establishing cell lines when whole blood is used.

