In addition to the collection of routinely obtained clinical data and the results of routine laboratory investigations, this research includes taking an extra blood (4-11 ml depending on the visit) and urine, special handling of the liver biopsy and surgical specimens, and samples of blood from parents. There will be no costs to the patient or their insurance for any research-related data collection, including the developmental

assessments, or special laboratory investigation. The expenses for the storage and handling of the extra research blood and urine samples and research handling of the liver sample are covered by the research.

For each scheduled follow up visit the parents or guardians will receive the equivalent of \$15-20 (amount and method of payment – cash, gift certificate or check – to be determined by the clinical site) to reimburse them for parking, meals or other expenses that they may have related to the visit.

10. Ethical Concerns and Informed Consent

There are minimal physical and psychological risks from being in this study. For the *database study*, the risks of venipuncture at the time of the blood draws are pain, bruising or superficial phlebitis.

The risks of genetic information being revealed by any future investigations in the Consortium are very slight since the blood samples will be de-identified prior to being deposited in the repository; that is only a research study number will be included in the database and all dates will be converted into ages by the DCC prior to dissemination to the repository or to any laboratory conducting genetic studies. While the study is ongoing, the clinical site will maintain a link between the research study number and the subject's identity. However, this information will not be contained in any data file that is transmitted to the DCC or to the repository. When the study ends (or ChiLDREN ceases to exist), each clinical site will destroy the linkage between the research study number and the subject's identity.

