If there is a loss of confidentiality, the risks include: that knowledge of a genetic risk may be emotionally stressful to a family member, that this might change eligibility for new health, disability or life insurance, that there may be unforeseen paternity issues, and that genetic testing may reveal information regarding health risks to other members of the family who are living or not yet born. The tissue in the Repository will be extra tissue removed at the time of clinically indicated surgery or liver biopsy and will not compromise the clinical care of the patient.

Methods Taken to Reduce Patient Risks: The study anticipates no excessive risks to the patients, except the possible pain associated with blood draws. EMLA cream may be applied to sites of all blood draws and intravenous lines to minimize pain with these procedures. Psychological risks will be minimized by careful explanation of the risks and by maintaining complete confidentiality and data security.

Informed Consent: A common template for the informed consent form will be used by all of the centers, modifying the content or format as necessary to meet the requirements of their respective institutional human subjects committees. The subject will retain a signed consent form; one will be retained for the subject's chart; and one will be included in the research records.

11. References

4. Ohi R. Biliary atresia. A surgical perspective. *Clin Liver Dis* 2000; 4:779-804.
6. Desmet VJ. The Cholangiopathies. In: Suchy FJ, Sokol RJ, Balistreri WF, eds. *Liver Disease in Children*. Philadelphia: Lippincott, Williams & Wilkins, 2001:39-62.

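### Section 8 names phlebotomy as the only source of study-related serious events, although Section 4.5 permits a research-only skin excision

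*Supplement*

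**What the plan says.** The opening of Section 8 (Adverse Events) states that "in general there are no adverse events that can be attributed to it except at the time of blood draws", and then, without a qualifier: "The only serious adverse events related to the performance of this study are those related to phlebotomy".

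Section 4.5 (Specimens to be Collected) sets out a further procedure. "In children where consent for DNA and cell lines has been obtained, at the time of transplantation or surgery the following may be obtained": "Skin from the surgical incision to establish cell lines and extract DNA". The note beneath it covers the case where the investigator doubts that whole blood will be available. Then "skin from the incision (approximately 1cm in length and 3 mm in width) may be removed and sent to the repository". The note adds that "This method should be used rarely", because cell lines grow less reliably from skin than from blood.

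Section 10 (Ethical Concerns and Informed Consent) gives the physical risks as follows: "the risks of venipuncture at the time of the blood draws are pain, bruising or superficial phlebitis". On tissue it says: "The tissue in the Repository will be extra tissue removed at the time of clinically indicated surgery or liver biopsy".

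**The concern.** The skin strip replaces a research blood sample. No diagnostic or therapeutic purpose is given for it, so it is a study procedure in the ordinary sense, and an invasive one in an infant or child with liver disease. A protocol that authorises it should not also state that only phlebotomy can give rise to a related serious event.

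What is at stake is the attribution of wound events. Infection, bleeding or breakdown at the incision is also a recognised consequence of the operation itself. Where research and clinical surgery share one wound, the assessor has to make a judgement, and Section 8 gives that assessor two different answers. A secondary matter is that the protocol's account of physical risk is incomplete.

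**Working it through.** No arithmetic bears on this point, and the plan gives no figure to reproduce. The check sets the relevant statements side by side.

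1. **Is the excision a research procedure?** Section 4.5 gives its purpose as cell lines and DNA, makes it depend on consent for those uses, and treats it as a fallback for blood. The other surgical specimens in Section 4.5 (liver, biliary remnant, lymph node and so on) are limited to material removed for clinical reasons and left over after diagnosis. The skin strip carries no such limit. It is research-only.

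2. **Does the Section 8 sentence cover it?** No. The sentence before it is worded as an expectation, but the sentence itself is categorical and names phlebotomy alone.

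3. **Does the rest of Section 8 agree with that sentence?** No. Section 8 goes on to define relatedness as attribution to the study procedures, without limiting these to blood draws. It requires an event to be treated as related when causation cannot be excluded. A wound event that might stem from the skin strip is therefore related under the rule and unrelated under the sentence. The text does not say which prevails. It then refers back to the earlier statement and repeats that attributable events are very unlikely.

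4. **Could such an event be serious?** Yes. Section 8 counts a prolonged hospital stay as serious, so an incision infection that delays discharge would qualify.

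5. **Does the risk text mention it?** Section 10 lists venipuncture risks and, under risk reduction, excepts only pain from blood draws. Section 9, in describing what the research adds to routine care, lists extra blood and urine, handling of biopsy and surgical specimens, and parental blood. Neither section mentions skin.

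6. **Do the tissue statements fit?** Section 4.4, item 28, restricts tissue specimens to tissue taken out in the course of clinical care and beyond diagnostic need. The skin strip does not meet that. The Section 10 statement is less clear-cut: skin taken during a clinically indicated operation can be read as falling within its words, although the description of extra tissue suggests surplus rather than a purpose-cut sample.

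**The case against.** The strongest reply is that Section 8 mostly expresses an expectation and that its operative rule already gives the right answer. Much of this stands, and it rules out several stronger readings.

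- **A reader might infer that wound events are classified in advance as unrelated.** The documents do not support this. The causality rule in Section 8 covers study procedures in general and points to related. The categorical sentence can mislead, but it does not settle the classification.
- **A reader might infer that such events would not reach the Safety Monitor or the DSMB.** Section 8.2 has investigators report serious unexpected events and sets no relatedness condition. The online report alerts the Safety Monitor, who summarises the case for the DSMB Chair. One narrower weakness remains: an incision infection or bleed could be regarded as clinically expected and so not expedited. That turns on expectedness, not on the phlebotomy sentence alone.
- **A reader might infer that these events would not be captured at all.** Section 4.4 collects post-operative complications at discharge (item 12, including infection and haemorrhage), sentinel events between visits (item 25), and complications after transplant. The attribution label is at risk; the record of the event is not.
- **A reader might infer that parents are not told of the risk.** This cannot be established. The consent pages are not available, skin may be taken only with consent for DNA and cell lines, and Section 4.2.4 says the consent covers the risks of participation. The omission is shown only for the protocol's own risk text.

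It is also fair to say that no aim, outcome or analysis depends on the skin sample. What survives is a categorical safety statement that the protocol's own procedures show to be incomplete, set against a rule in the same section that contradicts it.

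**Conclusion.** The inconsistency is real and should be corrected. The phlebotomy-only sentence in Section 8 conflicts with the skin excision in Section 4.5 and with the causality rule later in Section 8. It could lead an assessor to attribute an incision complication wholly to the clinical operation. The physical-risk text in Section 10 omits the procedure. The tissue statement in Section 4.4 does not fit it, and the one in Section 10 fits it poorly.

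The impact is small. The strip is about 10 mm × 3 mm = 30 mm², is taken from an incision already made for surgery, requires consent, and is meant to be rare. The protocol gives no expected number of such samples, so the number of children affected cannot be stated. The conclusion assumes that the skin is taken for research only, which is how Section 4.5 describes it. It assumes nothing about the consent form.

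**What to change.** - In Section 8, name research skin sampling alongside phlebotomy as a possible source of related adverse and serious adverse events, and state that the causality rule in the same section governs every relatedness judgement, including complications at an incision from which research skin was taken.
- In Section 10, add the skin excision to the physical risks.
- Reconcile the tissue statements in Section 4.4 (item 28) and Section 10 with Section 4.5, so that skin taken for cell lines and DNA is described as what it is.
- Check that the common consent template agrees with the amended text.

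The change is to wording only and affects neither clinical care nor the analysis. Its running cost is a few more relatedness assessments.

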8.1 Data Safety Monitoring Board

The National Institutes of Health have set up a Data Safety Monitoring Board (DSMB) to oversee this study. The Data and Safety Monitoring Board (DSMB) will act in an advisory capacity to NIDDK to monitor patient safety and evaluate the ability of the ChiLDREN to achieve its research goals. Members of the DSMB are independent of the study investigators and represent disciplines related to liver disease, biostatistics and epidemiology, as well as possibly having a lay member. The DSMB will meet every six months or more frequently if requested by the Chair of the DSMB or the NIDDK Program Director, either in person or by teleconference.

8.2 Reporting of Serious Adverse Events

Each clinical investigator is responsible for reporting serious unexpected adverse events to the IRB at their institution, to the Safety Monitor, and to the NIH Program Director in an expedited manner. In general, when first informed of a serious adverse event, the investigator or designee will log into the ChiLDREN website and complete the Serious Adverse Event Form online. Upon receipt of a SAE notification the system will generate an email to notify the Safety Monitor, the Principal Investigator at that clinical site, the NIH Program Director and the DCC. The Safety Monitor will log in and read the report. If he has questions, he will contact the site and request clarification. After clarification is received, he will summarize the case and report it to the Chair of the DSMB, the NIH Program Director and the DCC. The Safety Monitor, the Chair of the DSMB and the NIH Program Director will determine whether the case should be reported to the IRBs at all the institutions participating in the trial. The Chair of the DSMB or the NIH Program Director can convene an emergency meeting of the DSMB as necessary.

Every three months, the data coordinating center will provide interim reports to the DSMB and the NIH Program Director. The contents of the report are determined by the DSMB. Additions and other modifications to these reports may be requested by the DSMB on a one-time or continuing basis. Interim data reports generally consist of two parts. Part 1 (Open Session Report) provides information on study aspects such as accrual, baseline characteristics, and other general information on study status. Part 2 (Closed Session Report) may contain data on study outcomes, including safety data. The DSMB will meet every six months to discuss the findings and to make a recommendation to the NIH regarding continuation, modification or termination of the study. Additional reports or meetings of the DSMB may be required at the discretion of the Chair of the DSMB or the NIH Program Director.

9. Costs and Payments to Participants

In addition to the collection of routinely obtained clinical data and the results of routine laboratory investigations, this research includes taking an extra blood (4-11 ml depending on the visit) and urine, special handling of the liver biopsy and surgical specimens, and samples of blood from parents. There will be no costs to the patient or their insurance for any research-related data collection, including the developmental

assessments, or special laboratory investigation. The expenses for the storage and handling of the extra research blood and urine samples and research handling of the liver sample are covered by the research.

For each scheduled follow up visit the parents or guardians will receive the equivalent of \$15-20 (amount and method of payment – cash, gift certificate or check – to be determined by the clinical site) to reimburse them for parking, meals or other expenses that they may have related to the visit.

10. Ethical Concerns and Informed Consent

There are minimal physical and psychological risks from being in this study. For the *database study*, the risks of venipuncture at the time of the blood draws are pain, bruising or superficial phlebitis.

The risks of genetic information being revealed by any future investigations in the Consortium are very slight since the blood samples will be de-identified prior to being deposited in the repository; that is only a research study number will be included in the database and all dates will be converted into ages by the DCC prior to dissemination to the repository or to any laboratory conducting genetic studies. While the study is ongoing, the clinical site will maintain a link between the research study number and the subject's identity. However, this information will not be contained in any data file that is transmitted to the DCC or to the repository. When the study ends (or ChiLDREN ceases to exist), each clinical site will destroy the linkage between the research study number and the subject's identity.

If there is a loss of confidentiality, the risks include: that knowledge of a genetic risk may be emotionally stressful to a family member, that this might change eligibility for new health, disability or life insurance, that there may be unforeseen paternity issues, and that genetic testing may reveal information regarding health risks to other members of the family who are living or not yet born. The tissue in the Repository will be extra tissue removed at the time of clinically indicated surgery or liver biopsy and will not compromise the clinical care of the patient.

Methods Taken to Reduce Patient Risks: The study anticipates no excessive risks to the patients, except the possible pain associated with blood draws. EMLA cream may be applied to sites of all blood draws and intravenous lines to minimize pain with these procedures. Psychological risks will be minimized by careful explanation of the risks and by maintaining complete confidentiality and data security.

Informed Consent: A common template for the informed consent form will be used by all of the centers, modifying the content or format as necessary to meet the requirements of their respective institutional human subjects committees. The subject will retain a signed consent form; one will be retained for the subject's chart; and one will be included in the research records.

11. References

4. Ohi R. Biliary atresia. A surgical perspective. *Clin Liver Dis* 2000; 4:779-804.
6. Desmet VJ. The Cholangiopathies. In: Suchy FJ, Sokol RJ, Balistreri WF, eds. *Liver Disease in Children*. Philadelphia: Lippincott, Williams & Wilkins, 2001:39-62.
